5.6 Concomitant Medications

Any medicinal product, prescribed or OTC, including herbal and other nontraditional remedies, is considered a concomitant medication. Patients should stay on stable regimen of other concomitant medications for the treatment of SLE (eg, analgesics, NSAIDs, statins, ACE

inhibitors/ARBs and other antihypertensive drugs), unless changes in these treatments are clinically indicated. Use of any other drugs for non-SLE conditions, including over-the-counter medications and herbal preparations, should remain stable unless change or addition is clinically necessary. Discussion with the medical monitor prior to initiation of new medication is strongly recommended. Any concomitant therapies must be recorded on the eCRF. Prior and concomitant medication use will be recorded for the 30 days prior to screening until the last follow-up visit. In addition, historical treatment for SLE (including immunosuppressant, anti-malarial, corticosteroid, and/or biologic agent) will be recorded for the 48 weeks prior to screening in the eCRF.

5.6.1 Oral Corticosteroid Dose

Prior to randomization, oral CSs (prednisone or prednisone equivalent), may be used in accordance with the investigator's clinical judgment and best standard of care. See [APPENDIX 3](#) for examples of equivalents.

A maximum daily dose of 30 mg/day of oral CS will be acceptable for eligibility for the study, however, the daily dose must be tapered down to a maximum of 10 mg/day for at least 5 days prior to Day 0 (randomization day).

After Day 0 (after initiation of study therapy), no up-titration above 10 mg/day is allowed except for up to 1 CS burst for increased disease activity.

Tapering of steroids during the course of the study will be encouraged and should be evaluated at all visits.

- Once a patient has received the first dose of study drug, prednisone (or prednisone equivalent) may be tapered down at the discretion of the investigator
 - Tapering is allowed after randomization except within 60 days of the primary (Day 210) and secondary (Day 120) endpoint assessments. Between Day 60 and Day 120, and between Day 150 and Day 210, oral CS doses must be held constant otherwise the patient will be declared a non-responder in efficacy assessments.

A maximum of 1 oral CS “burst” for increased SLE disease activity will be allowed during the study between Day 0 and Day 60, according to the following:

- An oral CS “burst” between Day 0 and Day 60; (an increase of ≤ 40 mg/day of prednisone or equivalent), which must be tapered down to a maximum of 10 mg/day within 2 weeks of initiation of the “burst”
 - Alternatively, a single intramuscular (IM) dose of methylprednisolone (40 mg or equivalent) is permitted
 - The course of the oral CS “burst” is not permitted to extend beyond Day 60

Treatment with inhalational CS therapy (eg, for asthma), or by any other route, is allowed. Other concomitant medications for SLE need to be taken at stable doses as per the inclusion criteria ([Section 5.4](#)).

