8 STATISTICS

The following analyses are planned:

- An IA will be performed during the last cohort of the MAD phase to determine dose selection for the POC phase.
- The final analysis will be performed when all patients have completed the safety follow-up or withdrawn from the study.
- Safety analyses will be performed for DMC reviews throughout the study to evaluate dose escalation decisions and accumulating safety data. The frequency and details of the

content and format of the safety review meetings will be described in the SAP and/or DMC charter.

All statistical analyses will be performed using Statistical Analysis Software (SAS[®]) Version 9 or higher.

The following standards will be applied for the analysis unless otherwise specified. Data will be summarized descriptively by treatment and overall for each study phase. For the MAD phase, BOS161721 will be summarized overall and by each dose level, and placebo patients from each cohort will be combined. Select parameters will be summarized using patients from both study phases. Statistical testing will be performed on data from the Phase 2 study only.

Continuous data will be summarized using number, mean, standard deviation (SD), 25th and 75th percentiles, minimum, median, and maximum. Categorical data will be summarized by treatment group using frequency tables (number and percentage). Time to event data will be summarized using counts, medians, 25th and 75th percentiles, and standard error. All data will be listed for all patients.

Statistical inference will be based on a 2-tailed test with an overall 0.10 level of significance, unless stated otherwise.

The effects of noncompliance, background therapy use, treatment discontinuations, premature withdrawal from study and covariates will be assessed to determine the impact on the general applicability of results from this study. Exploratory analyses of the data will be conducted as deemed appropriate. Any deviations from the planned analyses will be described and justified in the final integrated CSR.

Protocol deviations and prohibited medications that define medication failures will be fully assigned and documented before database lock and unblinding.

Further details of the analysis, including the handling of missing data, transformations and other data handling procedures will be provided in the SAP.

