8.2.3 Primary Efficacy Endpoint(s)

The proportion of patients who achieve a SRI-4 response at Day 210 will be assessed via Pearson's chi-squared analysis. The primary efficacy endpoint will be analyzed using the FAS and if needed repeated in the PP analysis set. Missing values will be addressed by employing a last observation carried forward (LOCF) analysis. Other imputation methods may be employed as a sensitivity analysis and will be described in the SAP. Additional analyses exploring impact of baseline factors such as baseline disease severity, race, and other characteristics may be performed.

Patients that received prohibited medications or unallowable CS usage as described in [Section 4.6](#) will be considered "medication failures" and will be treated as non-responders for the primary efficacy analysis. Patients that received an allowable CS burst but having missing data at Day 210 will considered a medication failure and will be treated as non-responders for the primary efficacy analysis. The determination of medication failures will be reviewed using blinded data and finalized prior to unblinding.

The superiority of BOS161721 relative to placebo will be evaluated. If the proportion of SRI-4 responders for the selected POC dose in BOS161721 arm is higher than that of the placebo arm, then BOS161721 will be considered superior to placebo if the 2-sided p-value is less than or

equal to 0.10. Secondary and exploratory endpoints for this POC study will be evaluated based on the same statistical hypothesis.

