APPENDIX 7 PROTOCOL SUMMARY OF CHANGES

The protocol summary of changes was moved to the end of the protocol for easier readability.

Significant changes are described in the table below. Changed text is displayed for the first major occurrence only. Deleted text is presented in strikethrough format, and added text is presented in bold format.

Section	Description of Changes	Rationale
Global	Add: Added ' Protocol Date and Version: 21 March 2018; V3.0 ' to the header.	Administrative
Global	Change: Changed Version number from V2.0 (Amendment 1) to V3.0 (Amendment 2) and Version date from 14 November 2017 to 21 March 2018 .	Administrative
Global	Change: Changed subjects to patients .	Replaced 'subjects' to 'patients' since the enrolled participants are with SLE condition
Global	Made administrative and editorial (formatting, typographical, and grammatical) updates.	Administrative
PROTOCOL SUMMARY, Background and Rationale	Add: The Phase 2 portion will be a proof of concept (POC) study, where dose selection will be based on the data monitoring committee (DMC) and sponsor's assessment of safety, tolerability, immunogenicity, and PK and PD data from the MAD study of 30 patients treated with BOS161721/placebo	Clarification that POC dose selection will be based on DMC and sponsor assessment
PROTOCOL SUMMARY, Objectives and Endpoints	The objectives and endpoints sections were combined together and are now represented in a table format in order to demonstrate which endpoints correspond to each objective. Only primary and secondary objectives and endpoints are listed within the synopsis. Additional edits were made to some objectives and endpoints. Some new endpoints were added to the study. An exploratory objective, to examine PK and PD effects of BOS161721 in subjects with mild to moderate SLE, was changed to 'secondary objective'. Changes to the objectives and endpoints are noted below: MAD Phase 1b Study	Updated for clarity and to provide a comprehensive list of endpoints identified in the protocol

Section	Description of Changes	Rationale
OBJECTIVES	ENDPOINTS	
Primary		

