5.5 Exclusion Criteria

Patients presenting with any of the following will not be included in this study:

1. Drug-induced SLE, rather than “idiopathic” SLE
2. Other systemic autoimmune disease (eg, erosive arthritis, rheumatoid arthritis [RA], multiple sclerosis [MS], systemic scleroderma, or vasculitis not related to SLE)
 - a. RA-Lupus overlap (Rupus), and secondary Sjögren syndrome are allowed
3. Any major surgery within 6 weeks of study drug administration, (Day 0), or any elective surgery planned during the course of the study

4. Any history or risk for tuberculosis (TB), specifically those with:
 - a. Current clinical, radiographic, or laboratory evidence of active TB
 - b. History of active TB
 - c. Latent TB defined as positive QuantiFERON-TB Gold In-Tube (QFT-G) or other diagnostic test in the absence of clinical manifestations. Latent TB is not excluded if the patient has documented completion of adequate course of prophylactic treatment with regimen recommended by local health authority guideline, or the patient has started treatment with isoniazid, or other regimen recommended by local health authority guidelines for at least 1 month before Day 0 and continues to receive the prophylactic treatment during study until the treatment course is completed.
5. Active or unstable lupus neuropsychiatric manifestations, including but not limited to any condition defined by BILAG A criteria, with the exception of mononeuritis multiplex and polyneuropathy, which are allowed
6. Severe proliferative lupus nephritis, (WHO Class III, IV), which requires or may require induction treatment with cytotoxic agents or high dose CS
7. Concomitant illness that, in the opinion of the investigator, is likely to require additional systemic glucocorticosteroid therapy during the study, (eg, asthma), is exclusionary
 - a. However, treatment for asthma with inhalational CS therapy is allowed
8. Use or planned use of concomitant medication outside of standard of baseline treatment for SLE from Day -1 or for any time during the study. (See [Section 5.6](#) for prohibited concomitant medication)
9. Active and clinically significant infection (bacterial, fungal, viral, or other) within 60 days prior to first dose of study drug. Clinically significant is defined as requiring systemic antibiotics or hospitalization
10. A history of opportunistic infection, or a history of recurrent or severe disseminated herpes zoster or disseminated herpes simplex within the last 3 years

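### The steroid section's allowance for corticosteroid by any other route conflicts with its own limits and, if still in V3.0, leaves late intra-articular and arguably IV steroid not clearly a medication failure

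*Protocol*

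**What the plan says.** The steroid rules are in V2.0 Section 5.6.1, which corresponds to V3.0 Section 4.6.1. The copy available contains only the last part of V3.0, so the V2.0 text is the latest shown.

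Section 5.6.1 of V2.0 sets these rules:
- After Day 0, "no up-titration above 10 mg/day is allowed except for up to 1 CS burst for increased disease activity".
- One oral burst is permitted between Day 0 and Day 60. As the alternative, "a single intramuscular (IM) dose of methylprednisolone (40 mg or equivalent) is permitted".
- Oral doses are frozen from Day 60 to Day 120, and again later: "between Day 150 and Day 210, oral CS doses must be held constant otherwise the patient will be declared a non-responder in efficacy assessments".
- The closing paragraph says: "Treatment with inhalational CS therapy (eg, for asthma), or by any other route, is allowed". The same sentence stands in V1.0.

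The list of prohibited treatments in V2.0 Section 5.6.2 names no corticosteroid by any route. In V3.0, Section 8.2.3 opens the definition of a medication failure with "Patients that received prohibited medications or unallowable CS usage as described in" Section 4.6, and counts such patients as non-responders. V3.0 Section 8 adds that "prohibited medications that define medication failures will be fully assigned and documented before database lock and unblinding".

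**The concern.** Section 8.2.3 does not define unallowable steroid use itself; it takes the definition from the concomitant-medication section. If that section says that every non-oral route is allowed, a reviewer classifying cases has no clear textual basis for calling a joint injection, or arguably an IV pulse, a failure.

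This bears on the primary endpoint. SRI-4 needs a fall of at least 4 points in SLEDAI-2K (V3.0 Section 6.3.4.1), and SLEDAI-2K covers the visit and the preceding 30 days (V3.0 Section 6.3.1). Arthritis is one of the clinical components that can qualify a patient at entry. Steroid given after Day 60 and before the final look-back could suppress scored activity and be counted as response. A change in oral dose between Day 150 and Day 210 makes the patient a non-responder, so similar rescue would be scored differently by route.

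The sponsor has already acted against this kind of use. The V2.0 summary of changes removed the later burst, with its IM option, because it conflicted with study endpoints.

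**Working it through.** **Texts by route, after Day 60**

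| Route | Text that allows | Text that limits |
|---|---|---|
| Oral | none | 10 mg/day cap; burst ends by Day 60; dose holds with non-responder rule |
| IM | open sentence | one dose only, as the alternative to the Day 0-60 burst |
| IV | open sentence | none that names IV; the cap, exclusion 7 and the log rationale point against it |
| Intra-articular | open sentence | none found |

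For IM, the specific one-dose rule should prevail, but the open sentence contradicts it. For IV the texts conflict. For intra-articular use the permission stands alone.

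**Window.** The SLEDAI-2K look-back at Day 210 starts at 210 - 30 = Day 180. The exposed period is therefore after Day 60 and before about Day 180, and the benefit must last to Day 210. The documents give no duration of effect.

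**The plan's own power.** V3.0 Section 8.1 gives 65% versus 40%, 2:1 allocation, 132 evaluable patients (88:44), two-sided 0.10, Pearson chi-squared, and claims more than 80%.
- Pooled rate: (88 × 0.65 + 44 × 0.40)/132 = 74.8/132 = 0.567.
- Null SE: √[0.567 × 0.433 × (1/88 + 1/44)] = 0.0915.
- Alternative SE: √[0.65 × 0.35/88 + 0.40 × 0.60/44] = 0.0897.
- z = (0.25 - 1.645 × 0.0915)/0.0897 = 1.11, so power is 0.866.
- Exact binomial enumeration of the same test gives 0.863. The claim reproduces.

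**Illustration.** The documents give no rate of IV or intra-articular use, so the shares below are assumptions. Let a and p be the percentage points of all active and all placebo patients who become responders through uncounted steroid. The rates are then 65 + a and 40 + p. Power is by exact enumeration, 88:44, rejection favouring active.

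| a | p | Rates (%) | Power |
|---|---|---|---|
| 0 | 0 | 65 v 40 | 0.863 |
| 5 | 5 | 70 v 45 | 0.875 |
| 10 | 10 | 75 v 50 | 0.890 |
| 0 | 2 | 65 v 42 | 0.809 |
| 0 | 5 | 65 v 45 | 0.709 |
| 2 | 5 | 67 v 45 | 0.785 |
| 5 | 10 | 70 v 50 | 0.731 |
| 5 | 2 | 70 v 42 | 0.930 |

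Power is 0.80 at p = 2.30 when a = 0, and at p = 13.55 when a = 10. The excess of p over a is 2.3 and 3.55 points, or 0.023 × 44 = 1.0 and 0.0355 × 44 = 1.6 placebo patients.

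With no drug effect and equal conversion, rejection favouring active is 0.0485 at 40% v 40% and 0.0477 at 45% v 45%. Type 1 error is not inflated.

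**The case against.** The strongest reply is that the permission is V2.0 text and the medication-failure rule is V3.0 text, and no version shown contains both. The V3.0 log goes from Section 4.4 to Section 5.1 without an entry for 4.6, but its stated scope is limited: "Significant changes are described in the table below". On the text shown it is also incomplete. Whole blood RNA is in the V2.0 list of pharmacodynamic assessments (Section 7.6) and absent from the V3.0 list (Section 6.6), with no logged deletion. This stands, and it makes the point conditional.

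The second reply is about context. A reader might infer that IV steroid after Day 60 is plainly permitted. The documents do not support that. A single permitted IM dose would be pointless if every non-oral route were open. The 10 mg/day cap names no route, although it sits under a heading on oral dose. Exclusion 7 bars illness likely to need extra systemic steroid and then allows inhaled steroid for asthma, the same example the open sentence uses, which suggests that a carve-out for local, non-SLE use was meant. Section 8.2.3 speaks of steroid use in general, not only oral. The V2.0 log rationale treats steroid outside the permitted windows as a protocol violation. Exclusion 8, which bars "concomitant medication outside of standard of baseline treatment for SLE from Day -1 or for any time during the study", adds less, because it refers back to Section 5.6 for what is prohibited. Together these make IV a conflict of texts, not an open permission. None of them mentions joint injections, and a protocol violation is not in itself a medication failure.

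The third reply is that failures are settled on blinded data before unblinding. That protects against bias in classification. It does not tell reviewers how to class a use that the governing section calls allowed. Whether a joint injection ought to be a failure is partly a design choice; the case for it is consistency with the oral hold.

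**Conclusion.** The point holds as a wording conflict that feeds the primary endpoint definition, conditional on V3.0 Section 4.6.1. The open sentence contradicts the single-IM rule, conflicts with several indications against IV rescue, and is unopposed for intra-articular steroid. If it survives in V3.0, late intra-articular use, and arguably IV use, is not clearly a medication failure under Section 8.2.3.

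A reader might infer from the table that the trial loses power or overstates the drug's effect. The documents do not support either conclusion. The conversion shares are assumed, the direction is unknown, and equal conversion neither lowers power nor inflates type 1 error. The figures show only that a small imbalance would matter: an excess of one to two placebo patients in 44 takes power from 0.863 to 0.80, while an excess on active widens the apparent difference (28 points at 70% v 42%). Severity is low to moderate.

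**What to change.** First confirm whether the sentence is still in V3.0 Section 4.6.1. If it is:
- Limit it to inhaled, topical, ophthalmic or other local non-articular steroid.
- State in the same section that IV, IM or intra-articular steroid outside the one permitted Day 0-60 burst is not allowed.
- In Section 8.2.3, name such use up to Day 210 as a medication failure, scored as non-response. A patient who needs the treatment still receives it and is still followed.

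The cost is a corrected passage in Section 4.6.1 and one sentence in Section 8.2.3, with no change to sample size. The eCRF must capture the route and date of each steroid dose; V2.0 Section 5.6 requires concomitant therapies to be recorded but does not mention route. The downside is that a few more patients will be classed as non-responders.

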5.6.2 Other Prohibited and/or Restricted Treatments

Prohibited and/or restricted medications taken prior to study drug administration and during the study are described below, and washout requirements are provided in [APPENDIX 4](#). Medications taken within 30 days prior to screening must be recorded on the eCRF.

1. Prior exposure to BOS161721
2. Patients who have received treatment with anti-CD20 monoclonal antibodies within 6 months of screening; recovery of B cells (CD19+) must be documented (record absolute number of CD19+ B cells)
3. Patients who have received treatment with cyclophosphamide within the 1 year prior to screening
4. Patients who have received treatment with cyclosporine (with exception of ophthalmic use), any other calcineurin inhibitor or other immunosuppressive medication not specified in the inclusion criteria (oral or topical) within 3 months of screening
5. Patients who are currently receiving or are scheduled to receive plasmapheresis or lymphapheresis therapy, or have received such therapy within 8 weeks prior to screening
6. Patients who have received any live vaccines within 30 days of screening. Note: Furthermore, live vaccines should not be used during the course of the study and within the 2 months following last dose. Other inactivated vaccines such as tetanus, etc, may be used according to local guidelines during treatment period
7. Patients who are scheduled or anticipated to have elective surgery during the course of the study
8. Initiation of new immunosuppressant or anti-malarial agent is not permitted. Note: Dose reduction or replacement may be allowed due to intolerability or shortage for patients on a stable dose prior to study initiation

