Blood samples were collected at every in-house study visit for BOS161721 concentration determinations. Blood samples were also collected for determination of IL-21 plasma levels (free and total). Safety was assessed based on the occurrence of treatment-emergent AEs, hepatic function abnormality, and acute and delayed hypersensitivity reactions. Other safety variables included electrocardiograms (ECGs), vital signs (blood pressure, heart rate, and temperature), safety laboratory assessments, blood sampling for ADAs, total IgG and IgM levels, CD4+ count, and full and targeted physical examinations. Overall, there were no clinically significant findings from this study, following an interim cut and review of the data at Day 90 postdose. Adverse events reported as related to the study drug, particularly infections, were expected for the compound, and there were no clinically relevant changes in laboratory and ECG results or vital signs. There was 1 serious adverse event (SAE; death due to pulmonary embolism) that occurred 127 days after a single administration of 240 mg SC dose of BOS161721. The causality of this single SAE was not attributed to study drug and further information can be found in the Investigator's Brochure. PK data from the SAD study demonstrates BOS161721 has an extended $t_{1/2}$ (provisional single dose data indicates this to be approximately 42-46 days) which supports evaluation of monthly dosing.

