1.2.3 Study Dose Selection

Doses have been selected for the multiple ascending dose (MAD) Phase 1 study based on a 90-day safety, tolerability, PK, and PD data review from the Phase 1 SAD study (BOS161721-01); the SDMT reviewed the blinded safety data from subjects for each dose cohort (8 cohorts, evaluating 1 [IV], 3 [SC], 10 [SC], 22 [IV], 30 [SC], 60 [SC], 120 [SC], or 240 [SC] mg), along with the accumulated safety and available PK/PD data from all subjects in the previous dose cohorts, to make a decision on whether to proceed to the next higher dose level, repeat a dose level, or stop dose escalation. Overall, there were no clinically significant safety or tolerability findings from this study.

Based on the Day-90 interim cut of the PK and biomarker data in the BOS161721-01 study, the recommended doses for evaluation in the MAD phase of this study are 20, 60, and 120 mg SC monthly. This dose recommendation is supported by evidence of linear PK with BOS161721 resulting in a median T_{max} of 6 days and an apparent terminal half-life of 44 days. Furthermore, pSTAT3 suppression, a marker of IL-21 target engagement, follows a similar time course of the mAb levels, with maximal and sustained suppression apparent with doses greater than 30 mg SC (Figure 1).

Figure 1. Individual pSTAT3 C_{min} Levels Versus Dose

IV = intravenous, pSTAT3 = phosphorylated signal transducer and activator of transcription 3; SC = subcutaneous

All doses selected for the MAD study are projected not to exceed the mean exposure of that achieved following the highest single dose of 240 mg SC administered in the Phase 1 SAD study. Cohort 1 will include randomized treatment to the 20 mg dose. Based on the staggered study design, the data monitoring committee (DMC) will perform a scheduled review of safety data and sequentially consider dose escalation for Cohorts 2 and 3. In addition, the DMC and Boston Pharmaceuticals will conduct a data review for the first interim analysis (IA1). At that time, a decision will be made to suggest which dose should be carried forward into the proof of concept (POC) Phase 2 study. This POC dose decision will be based on evaluation of the PK, safety (inclusive of dose-limiting toxicity [DLT]), and tolerability data (and available PD/biomarker data) from Cohorts 1, 2 and 3 from the MAD study (see [Section 4.1.1.1](#)).

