1.2.5.4 Infections

BOS161721 is expected to diminish the activity of T-cell, B-cell and NK-cell lines. Like other medications modulating immune response, BOS161721 may increase the potential risk for infection, including serious infections. IL-21 produced by CD4⁺ Th cells is required to sustain the anti-viral function of CD8⁺ T-cells against chronic viral infections. Nonclinical evidence suggests that the risk of chronic viral infection recurrence or increased severity may occur with IL-21 inhibition.³⁵

These conditions will be fully characterized with clinical descriptions and routine laboratory and/or specialty testing and treated where indicated with appropriate local standard of care.

Patients with a history of opportunistic infection, including recurrent or severe disseminated herpes zoster or disseminated herpes simplex within the last 3 years, or any other underlying pathology predisposing to serious infection, are excluded from studies with BOS161721 (for further details please refer to the current IB for BOS161721).

Patients will be assessed for hepatitis B, and C, and HIV-1/2 combination, at screening.

Cryptosporidium Infection

Cryptosporidium infection was noted in patients with an IL-21 receptor loss-of-function gene mutation and similar findings of cryptosporidium infection have been observed in immunosuppressed liver transplant and human immunodeficiency virus patients.^{36,37} Since

BOS161721 is expected to diminish the immunosurveillance activity of T-cell, B-cell, and NK-cell lines, a similar risk is biologically plausible with prolonged exposure to BOS161721.

Since the risk of opportunistic cryptosporidium infection increases with low levels of CD4+ T-cells,³⁷ patients with a CD4+ count $< 500 \text{ cell/mm}^3$ were excluded from the Phase 1 SAD study (BOS161721-01), and will be excluded from the proposed MAD/POC studies. Patients exposed to investigational product who develop diarrhea during the course of the study should immediately undergo an assessment for opportunistic infection including stool for ova and parasites and stool examination for cryptosporidium. Positive cryptosporidium in stool sample at screening is an exclusion. Treatment by the investigator where indicated should be guided by findings and be consistent with local standard of care.

Based on the limited Phase 1 SAD study (BOS161721-01), infections in subjects who received BOS161721 was not observed.

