5.7.2 Contraception

WOCBP must agree to follow instructions for method(s) of contraception for the duration of treatment with study drug plus 5 half-lives of study drug BOS161721 plus 30 days (duration of ovulatory cycle) for a total of 36 weeks after treatment completion.

Men who are sexually active with WOCBP must agree to follow instructions for method(s) of contraception for the duration of treatment with study drug plus 5 half-lives of study drug BOS161721 plus 90 days (duration of sperm turnover) for a total of 44 weeks after treatment completion.

Investigators shall counsel WOCBP and men who are sexually active with WOCBP on the importance of pregnancy prevention and the implications of an unexpected pregnancy. Investigators shall advise WOCBP and men who are sexually active with WOCBP on the use of highly effective methods of contraception. Highly effective methods of contraception have a failure rate of < 1% when used consistently and correctly.

At a minimum, patients must agree to the use of 1 method of highly effective contraception from the following:

- Male condoms with spermicide
- Hormonal methods of contraception including combined oral contraceptive pills, vaginal ring, injectables, implants, and intrauterine devices (IUDs) such as Mirena[®] by patients who are WOCBP or a male patient's WOCBP partner. Women who are partner of men who are patients participating in the study may use hormone-based contraceptives as 1 of the acceptable methods of contraception since they will not be receiving study drug.
- IUDs, such as ParaGard[®]
- Vasectomy
- Complete abstinence, defined as complete avoidance of heterosexual intercourse, is an acceptable form of contraception. Women who are abstinent while participating in the study must continue to have pregnancy tests. Acceptable alternate methods of highly effective contraception must be discussed in the event that the patient chooses to forego complete abstinence.

Azoospermic men and WOCBP who are continuously not heterosexually active are exempt from contraceptive requirements. However, they must still undergo pregnancy testing.

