6.5 Premature Discontinuation

While patients are encouraged to complete all study evaluations, they may withdraw from the study at any time and for any reason. Every effort will be made to determine why any patient withdraws from the study prematurely. If the patient is unreachable by telephone, a registered letter, at the minimum, should be sent to the patient requesting him/her to contact the clinic.

All patients who withdraw from the study with an ongoing AE or SAE must be followed until the end of study or until the event is resolved or deemed stable, respectively.

If a patient withdraws prematurely after dosing, an end of treatment (EOT) visit should be performed (Day 180) and a last follow-up visit 90 days after dosing should be scheduled (Day 270). Safety follow-up visit procedures based on the Schedule of Assessments (see [Section 6.4](#)).

Patient participation may be terminated prior to completing the study and the reason recorded as follows:

- AE/SAE
- Protocol deviation
- Lost to follow-up
- Patient withdraws consent at their own request

- Investigator decision
- Decision by sponsor (other than AE/SAE, protocol deviation, or lost to follow-up)

Withdrawn patients may be replaced after discussion between the investigator or designee and sponsor.

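### The live-vaccine ban in V2.0 ends about 2.0 half-lives after the last dose (1.4 without the 90-day visit), a short margin that is clearest for the 120 mg regimen; 5 half-lives would be a cheap improvement

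*Protocol*

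**What the plan says.** Section 5.6.2 item 6 of V2.0 states that "live vaccines should not be used during the course of the study and within the 2 months following last dose"; V1.0 has the same sentence. The corresponding V3.0 section, 4.6.2, is not in the text at hand. The V3.0 log of significant changes (Appendix 7) lists no change to the vaccine item.

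Dosing is every 30 days from Day 0 to Day 180, and the last follow-up visit is Day 270. Section 6.5 also asks early withdrawers to attend a last visit 90 days after dosing.

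Section 1.2.3 reports linear PK, a half-life of 44 days and a Tmax whose median is 6 days. It adds that pSTAT3 suppression tracks the drug level over time. On how this depends on dose, it reports the result "with maximal and sustained suppression apparent with doses greater than 30 mg SC". Section 1.2.2.3 qualifies the half-life: "provisional single dose data indicates this to be approximately 42-46 days", from healthy subjects. The SC doses tested there were 3, 10, 30, 60, 120 and 240 mg.

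For contraception, section 5.7.2 requires the treatment period "plus 5 half-lives of study drug BOS161721 plus 30 days" for women, and 5 half-lives plus 90 days for men. Appendix 4 states that its washout times rest on 5 half-lives.

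**The concern.** The drug leaves the body slowly and accumulates over seven monthly doses, yet the ban is set in calendar months without reference to the half-life. Section 1.2.5.4 says that "BOS161721 is expected to diminish the activity of T-cell, B-cell and NK-cell lines", allows for serious infections, and notes that "risk of chronic viral infection recurrence or increased severity may occur with IL-21 inhibition". If much drug remains when the ban lapses, a patient could receive a live vaccine while IL-21 is still largely blocked.

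Detection would also be weak at that point. Under V3.0 section 6.2.2.7.2, SAEs are recorded to Day 270, and later ones are reported only if the investigator judges them related to study drug. What is at stake is patient safety after the last visit. No endpoint or analysis depends on it.

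**Working it through.** **Inputs (V2.0).** Half-life 44 days, linear PK, Tmax 6 days and the mark of doses above 30 mg SC (1.2.3); half-life range 42 to 46 days and doses tested (1.2.2.3); seven doses 30 days apart (4.1); regimens of 20, 60 and 120 mg (4.1.1); last visit 90 days after the last dose (6.4, 6.5). Two months is taken as 60 days.

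**The protocol's own 5-half-life figures reproduce.** (5 × 44 + 30)/7 = 35.7 weeks, stated as 36. (5 × 44 + 90)/7 = 44.3 weeks, stated as 44. So 44 days is the half-life the protocol itself works with.

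**Length of the ban.** The two terms are cumulative, so the later end applies.
- With the 90-day visit: 90/44 = 2.05 half-lives (1.96 to 2.14 for 46 to 42 days).
- Without it: 60/44 = 1.36 half-lives.

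**Level left after seven doses.** Superposition without an absorption phase:
- Decay per interval: r = 2^(−30/44) = 0.623.
- Accumulation: (1 − r^7)/(1 − r) = 2.558.
- At 90 days: 2.558 × 2^(−90/44) = 2.558 × 0.242 = 0.620 of a first-dose peak.
- With first-order absorption set to Tmax 6 days (ka = 0.631/day), the result rises by a factor of 1.127, to 0.699.

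Expressed as the single dose whose peak equals the level left at 90 days:

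| Regimen | Half-life 44 d | Half-life 42 to 46 d |
|---|---|---|
| 20 mg | 12.4 to 14.0 mg | 11.2 to 15.2 mg |
| 60 mg | 37.2 to 41.9 mg | 34 to 46 mg |
| 120 mg | 74.4 to 83.8 mg | 67 to 91 mg |

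**Against the pSTAT3 mark.** The statement concerns doses greater than 30 mg, and the next SC dose tested was 60 mg. The 120 mg regimen stays above 60 mg over the whole half-life range. The 60 mg regimen falls in the untested gap between 30 and 60 mg. The 20 mg regimen is below 30 mg.

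**Days after the last dose until the level reaches a mark**, as 44 × log2(dose × 2.558/mark), with absorption giving the upper figure:
- 120 mg to a 60 mg mark, and equally 60 mg to a 30 mg mark: 104 to 111 days (97 to 118 over 42 to 46 days), which is 14 to 21 days past the 90-day visit.
- 120 mg to a 30 mg mark: 148 to 155 days (139 to 164).

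**Other patients.** Without the 90-day visit, at 60 days after seven doses, the factor is 0.99 to 1.12: about 60 to 67 mg for the 60 mg regimen and 119 to 135 mg for the 120 mg regimen. For a withdrawer with one to six doses who attends the 90-day visit, the factor is 0.24 to 0.61 (0.27 to 0.68 with absorption), so a patient with few doses may be below either mark.

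**At 5 half-lives (220 days).** 2.558 × 2^(−5) = 0.080 (0.090 with absorption): 4.8 to 5.4 mg for the 60 mg regimen and 9.6 to 10.8 mg for the 120 mg regimen, at most 12.9 mg with a 46-day half-life.

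**The case against.** The main objection is to the benchmark. It is a dose, read from a figure of trough pSTAT3 by dose that is not shown. It does not define a concentration, still less a level at which live vaccination becomes safe. A reader might infer that both the 60 and 120 mg regimens are still at maximal suppression on Day 270. The documents do not support that for 60 mg, because 37 to 42 mg falls where no SC dose was tested. Equating a residual level with a single-dose peak is also an inference, from healthy subjects. If suppression persisted as levels fell from that peak, the level needed is lower and the shortfall longer, but the text cannot settle this.

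A reader might also see a contradiction with the contraception rule. There is none: that rule guards against a different risk. Nor does the ban end at 2 months for everyone; that term governs only a patient who leaves without the 90-day visit.

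Two further objections stand in part. The sentence is in superseded V2.0 text, and a log limited to significant changes makes its survival in V3.0 likely, not certain. And 220 days is longer than the pSTAT3 calculation requires, which supports about 104 to 155 days; the longer period rests on convention. The consent form and Investigator's Brochure are not shown and may already carry further advice.

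**Conclusion.** The point holds as a short safety margin. The V2.0 ban lapses at about 2.0 half-lives, or 1.4 without the 90-day visit. After a full course of 120 mg, the projected level at that time lies within the tested dose range for which the protocol reports maximal target suppression, and it stays there for roughly another two to three weeks on a 60 mg mark or about two months on a 30 mg mark. For 60 mg, maximal suppression at Day 270 is possible but unproven. For 20 mg the level is below the mark.

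This rests on linear PK, one-compartment superposition, a provisional single-dose half-life carried over to patients, and the reading of dose as a proxy for level. It does not show that vaccination at Day 270 would be unsafe. It is an optional improvement with no bearing on efficacy or its analysis.

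**What to change.** First check the V3.0 wording of section 4.6.2. If the sentence is unchanged, replace it with a ban on live vaccines during the study and for 5 half-lives (220 days, about 31 weeks) after the last dose. This follows the convention already used for contraception and washout, and is shorter than the 36 and 44 weeks of contraception. Leave the rule on inactivated vaccines as it is. State the period in the consent form and repeat it at each dosing visit, so that patients later lost to follow-up have been told.

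The cost is one protocol sentence, a line in the consent form and a line in the visit instructions, with no added data, visits or patients. The downside is that a completer waits 220 − 90 = 130 more days after Day 270 for a live vaccine, and compliance after that visit cannot be checked. The contraception advice already runs past the last visit in the same way.
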